8.2.7.1. Pregnancy Testing

Pregnancy testing is to be performed on all women unless they meet the criteria describing women not of childbearing potential, as outlined in Section 5.1. Participants who are pregnant will be discontinued from the study (Section 7.1.2).

Visits and Times

Urine pregnancy testing will be performed locally during designated scheduled visits through Week 156. The urine pregnancy test must be “negative” within 24 hours prior to administration of study drug.

Between visits, urine pregnancy tests are to be performed prior to monthly at-home dosing.

Urine pregnancy testing may be performed at additional time points during the treatment period and/or follow-up period at the discretion of the investigator, or if this is required by local regulations.

If a urine pregnancy test is not available, a local serum pregnancy test is an acceptable alternative.

Assessment of follicle-stimulating hormone levels can assist in determining if a woman meets the definition of “postmenopausal” as outlined in Section 5.1. Follicle-stimulating hormone can be optionally obtained during study entry procedures at the discretion of the investigator.

Follicle-stimulating hormone can also be optionally obtained during the study to determine postmenopausal status (see Section 1.3).

8.2.8. Hepatitis B Testing

HBV Screening and Interpretation

Participants with acute or chronic hepatitis B infection are excluded from the study (see Section 5.2).

Screening for HBV in this study is performed as follows: an initial test for hepatitis B surface antigen (HBsAg) and hepatitis B core antibody (HBcAb), followed by a test for HBV DNA in participants who are HBsAg-, HBcAb+. Participants testing HBcAb+ in the originator study do not need to have HBV full screening at Visit 1, but they will need to have HBV DNA testing at screening, as well as HBV DNA monitoring throughout the trial, as described below.

Exclusion Based on HBV Serology and HBV DNA Testing

Participants with the following screening test results will be excluded from the study (Section 5.2).

- HBsAg+, irrespective of HBcAb result, or
- HBsAg-, HBcAb+ with detectable HBV DNA.

Participants Potentially Allowed into the Study, Based on HBV Serology and HBV DNA Testing

Participants with the following screening test results may be eligible for inclusion, provided they meet the other study entry criteria:

- HBsAg-, HBcAb-, or
- HBsAg-, HBcAb+ with no HBV DNA detected.

Management of participants with the following HBV serology from the originator study or at Week 0 of AMAX (or found to have the following serology at any time during AMAX) will undergo HBV DNA monitoring as described in the SoA (Section 1.3):

- HBsAg-, HBcAb+, HBV DNA not detected

In addition, if such participants experience an elevated ALT or AST level $>3 \times$ ULN during the study, they must have an HBV DNA test and be managed appropriately based on the results of that test.

Management of Participants with Detectable HBV DNA during the Study

Please contact medical monitor for any scenarios not covered below.

If a participant develops detectable but not quantifiable HBV DNA:	

 • Withhold the study drug. • Repeat HBV DNA, HBsAg, ALT, AST, TBL within 2 weeks and again 2 weeks later, at the central laboratory, if possible. However, if central laboratory collection is not possible due to extenuating circumstances, and after consultation with the medical monitor, local laboratories may be used to facilitate the patient's compliance. Results should be reported in the Local Laboratory Tests CRFs under the Hepatic visit for tests where data collection fields exist. • If the repeat HBV DNA is undetectable, or detectable but not quantifiable, on 2 consecutive retests (for a total of 3 consecutive tests), and the participant remains asymptomatic^a with no elevation in liver tests^b, the study drug can be resumed with close monitoring of HBV DNA and liver tests. • The investigator should wait for the results of both HBV DNA tests before making a decision on resuming the study drug. • HBV DNA, ALT, AST, TBL should be monitored at least once-monthly in the 3 months after the last detectable HBV DNA result and every 3 months thereafter. • If one of the subsequent HBV DNA results again becomes detectable and not quantifiable, but the participant remains asymptomatic with normal liver tests, continue the study drug, and increase monitoring frequency of HBV DNA, ALT, AST, and TBL to once-monthly. • If one of the repeat HBV DNA results is detectable and quantifiable, follow the instructions below, for participants with detectable and quantifiable HBV DNA. 	
If a participant develops detectable and quantifiable HBV DNA:	

If the participant is asymptomatic^a and liver tests are not elevated^b:
 
 • Withhold the study drug. • Repeat HBV DNA, HBsAg, ALT, AST, and TBL within 2 weeks. • Inform the Lilly-designated medical monitor. • Refer to a hepatologist^c for further management, including initiation of a nucleoside/nucleotide analog (NA). 	
If the participant is symptomatic^a, or if ALT, AST, or TBL are elevated^b:
 
 • Withhold the study drug. • Repeat HBsAg, ALT, AST, and TBL within 48 to 72 hours to determine if the levels are increasing or decreasing. • Continue monitoring liver tests 1 to 3 times weekly according to the protocol requirements for treatment-emergent abnormal liver tests. • Inform the Lilly-designated medical monitor.


 Continue monitoring HBV DNA, HBsAg, ALT, AST, and TBL every 2 weeks. If HBV DNA is undetectable in 3 consecutive tests, and liver tests are not elevated^b, monitoring frequency can decrease to once every 1 to 2 months. 	
 Refer to a hepatologist for further management, including initiation of a nucleoside/nucleotide analog (NA). Continue monitoring HBV DNA, and HBsAg, every 2 weeks. If liver tests are back to baseline, and HBV DNA is undetectable in 3 consecutive tests, monitoring frequency can decrease to once-monthly.
--	--

Resumption of the study drug in participants with detectable and quantifiable HBV DNA:

Resumption of the study drug after interruption for detectable and quantifiable HBV DNA, can be considered only:

- in asymptomatic^a participants without concurrent elevated^b liver tests, or in whom there was a clear alternative cause for the elevations, and they have returned to baseline
- in consultation with the Lilly-designated medical monitor, and
- only after the participant was seen by a hepatologist^c and NA has been initiated.

If the above criteria are met:

- the study drug can be restarted 7 days after NA initiation.
- If NA was initiated and the study drug was resumed, HBV DNA, HBsAg, ALT, AST, and TBL should be monitored at least monthly initially.
- After HBV DNA is undetectable in 3 consecutive tests, monitoring frequency can be decreased to every 2 to 3 months.

Permanent discontinuation of the study drug in participants with detectable and quantifiable HBV DNA:

The study drug should be permanently discontinued if any of the following occurs:

- HBV DNA is detectable and quantifiable with concurrent elevation^b of ALT, AST, or TBL for which there is no clear alternate cause.
- HBV DNA is detectable and quantifiable with concurrent symptoms^a that are considered by the investigator to be related to HBV reactivation.
- HBV DNA viral load is >100 IU/mL on 2 or more tests.

HBV DNA is detectable and quantifiable, but participant does not start NA treatment.

Duration of HBV DNA monitoring and NA prophylaxis in participants with detectable and quantifiable HBV DNA:

- HBV DNA monitoring should continue for at least 6 months after the last dose of the study drug.
- If NA was initiated and the study drug was resumed, NA treatment and HBV DNA monitoring should continue for at least 6 months after the last dose of the study drug.
- The participant should be referred to a hepatologist^c for continued follow-up and management after study participation.

a Symptoms may include worsening fatigue, nausea, vomiting, abdominal discomfort, jaundice, fever, or rash.

b ALT, AST, or TBL elevation refers to elevations $\geq 2x$ ULN in participants with normal baseline or near normal baseline (i.e., $<1.5x$ ULN) or elevation $\geq 2x$ baseline in participants with elevated baseline (i.e., $\geq 1.5x$ ULN). In participants with Gilbert's syndrome, isolated hyperbilirubinemia may be up to 3x ULN provided that direct bilirubin is no higher than 30% of the total.

c A hepatologist may include a health care provider with recognized expertise in the assessment and management of viral hepatitis.

If the study drug must be discontinued per guidelines above, the participant will have an ETV. The participant will then enter the posttreatment follow-up period (Section 7.1). Prior to discontinuing investigational product (IP), the sponsor recommends that a hepatologist (or a physician with expertise in viral hepatitis) is consulted and that it is determined whether it is appropriate to start antiviral therapy prior to discontinuation of IP or any immunosuppressant or immunomodulatory therapy. However, study drug should not be administered until this consultation has been completed and after discussion with the medical monitor. Such participants should also receive appropriate follow-up medical care.

If HBV DNA is detected during the study, the investigator should consider using one of the following terms to report the AE:

- “Detectable HBV DNA” if HBV DNA is detected without an increase in aminotransferase levels.
- “Reactivation of hepatitis B” if HBV DNA is detected and quantifiable in concert with an increase in aminotransferase levels and/or symptoms and signs of liver disease.

8.2.9. Hepatitis C Testing

Participants with current hepatitis C infection are excluded from the study (see Section 5.2).

Screening for HCV in this study is performed as follows: an initial test for HCV antibody, followed by a test for HCV RNA if the HCV antibody test is positive. Participants with a positive HCV antibody test and detectable HCV RNA will be excluded from the study (Section 5.2).

Participants who test negative for HCV antibody will not be tested for HCV RNA and may be eligible for inclusion in the study.

Participants who have spontaneously cleared hepatitis C infection, defined as:

- a positive HCV antibody test, and
- a negative HCV RNA test, with no history of anti-HCV treatment,

may be eligible for inclusion in the study, provided they have no detectable HCV RNA on screening for this study.

Any participant with a history of hepatitis C infection who develops elevated ALT $>3 \times$ ULN within the study will be tested for HCV RNA.

Participants with a previous diagnosis of hepatitis C who have been treated with antiviral therapy and achieved a sustained virologic response may be eligible for inclusion in the study, provided they have no detectable HCV RNA at screening. Sustained virologic response is defined as an undetectable HCV RNA level 24 weeks after completion of a full, documented course of an approved, potentially curative antiviral therapy for HCV.

If a participant is diagnosed with hepatitis C during the study (detectable HCV RNA), the study drug will be discontinued, and the participant will have an ETV. The participant will then enter the posttreatment follow-up period (Section 7.1). Such participants should also receive appropriate follow-up medical care.

CCI

CCI

A large, bold, red text "CCI" is centered on a black rectangular background.

8.2.11. Depression, Suicidal Ideation, and Behavior Risk Monitoring

Suicide-related events (behavior and/or ideations) will be assessed at screening with the administration of the **CCI** [REDACTED]

Depressive symptomology will be assessed with the **CCI** [REDACTED] at the visits specified in the SoA (Section 1.3).

These assessments are described below, and further information is provided in Section 10.9, Appendix 9.

A large, bold, red text "CCI" is centered on a black rectangular background.

See Section 8.3.2.1 for information about AE collection relative to collection of the **CCI** [REDACTED]

See Section 7.1.2 for information regarding discontinuation of study drug for participants who have suicidal ideation or suicidal behaviors.

8.3. Adverse Events and Serious Adverse Events

Investigators are responsible for monitoring the safety of participants who have entered this study and for alerting Lilly or its designee to any event that seems unusual, even if this event may be considered an unanticipated benefit to the participant.

The investigator is responsible for the appropriate medical care of participants during the study.

The investigator remains responsible for following, through an appropriate health care option, AEs that are serious or otherwise medically important, considered related to the investigational product or the study, or that caused the participant to discontinue the investigational product before completing the study. The participant should be followed until the event resolves,

stabilizes with appropriate diagnostic evaluation, or is otherwise reasonably explained. The frequency of follow-up evaluations of the AE is left to the discretion of the investigator.

Lack of drug effect is not an AE in clinical studies, because the purpose of the clinical study is to establish treatment effect.

After the informed consent form (ICF) is signed, study site personnel will record via eCRF the occurrence and nature of each participant's pre-existing conditions, including clinically significant signs and symptoms of the disease under treatment in the study.

In addition, after the first dose of study drug, site personnel will record any change in the condition(s), including exacerbation of CD, and any new conditions as AEs. Also, if an AE occurs after signing the AMAX ICF, but prior to receiving investigational product, and is considered reasonably possibly related to an AMAX study procedure, the AE should be reported as an AE in AMAX. Any other events/diagnoses that start after signing AMAX consent but before first AMAX dosing should be recorded in the AMAX MH eCRF.

Investigators should record their assessment of the potential relatedness of each AE to protocol procedure or investigational product via eCRF.

The investigator will interpret and document whether or not an AE has a reasonable possibility of being related to study treatment, study device, or a study procedure, taking into account the disease, concomitant treatment, or pathologies.

A "reasonable possibility" means that there is a cause-and-effect relationship between the investigational product, study device and/or study procedure, and the AE. The investigator answers yes/no when making this assessment.

Planned surgeries and nonsurgical interventions should not be reported as AEs unless the underlying medical condition has worsened during the course of the study.

If a participant's investigational product is discontinued as a result of an AE, study site personnel must report this to Lilly or its designee via eCRF, clarifying, if possible, the circumstances leading to any dosage modifications or discontinuations of treatment.

Care will be taken not to introduce bias when detecting AEs or SAEs. Open-ended and nonleading verbal questioning of the participant is the preferred method to inquire about AE occurrences (see Section 8.3.2.1).

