2.2. Background

2.2.1. Disease State and Treatment Goals

Crohn's disease is a chronic disease of unknown etiology with environmental, genetic, and immunologic influences. Transmural inflammation affecting any part of the gastrointestinal tract from the mouth to the anus, usually appearing as discontinuous lesions, is a normal characteristic for CD (Baumgart and Sandborn 2007). Symptoms include chronic diarrhea (often bloody and containing pus or mucus), abdominal pain (AP), weight loss, fever, fatigue, anemia, rectal bleeding, and a feeling of fullness in the abdomen. Symptoms depend on the severity of the disease and location of the disease, with most patients experiencing an abscess, fistula, stricture, or an obstruction requiring surgical intervention. Relapsing–remitting symptoms, meaning that many patients have intermittent disease flares that are interspersed with periods of remission, are very common in CD (Lichtenstein et al. 2018).

Treatment goals in clinical practice are control of symptoms and healing of the intestinal mucosa. In clinical trials, these goals are reflected by assessing induction of response (typically within a 6-week to 12-week period) and maintenance of remission in the longer term (over 52 weeks and beyond of continuous treatment) as assessed by patient-reported outcomes (PROs), including a reduction in stool frequency (SF) and AP. In both clinical practice and in clinical trials, assessment of the response to therapeutic interventions includes endoscopy to assess improvement in the endoscopic appearance of the mucosa and healing of ulcers.

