 - the participant reports suicidal ideation or suicidal behaviors during the study.

Other Reasons

- Treatment noncompliance: CCI [REDACTED] (Section 6.4).
- Study participants and physicians may discontinue the study participation if they perceive no clinical benefit.

Participants discontinuing from the study drug prematurely for any reason will complete AE and other follow-up procedures as specified in the SoA (Section 1.3), Section 8.2 (Safety Assessments), and Section 8.3 (Adverse Events and Serious Adverse Events), including ETV and posttreatment follow-up visits (Visit 801 and Visit 802).

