9.4.4. Safety Analyses

Safety endpoints are better assessed in the context of combining the safety data from the originating study with the safety data from this study. All safety data from this study will be used as part of integrated summaries.

For the purposes of the CSR for Study AMAX alone, a listing and summary of SAEs and AEs leading to permanent discontinuation of study intervention will be created.

The primary safety objective of the study is to accumulate long-term safety data for inclusion in integrated assessments of mirikizumab.

Safety analyses will be performed in the safety population.

The safety data from this study will also be used as part of ongoing safety reviews.

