10.3.1.2. Events Meeting the AE Definition

- Any abnormal laboratory test results (hematology, clinical chemistry, or urinalysis) or other safety assessments (e.g., ECG, radiological scans, or vital signs measurements), including those that worsen from baseline, considered clinically significant in the medical and scientific judgment of the investigator (that is, not related to progression of underlying disease).
- Exacerbation of a chronic or intermittent pre-existing condition, including either an increase in frequency and/or intensity of the condition.
- New condition detected or diagnosed after study intervention administration, even though it may have been present before the start of the study.
- Signs, symptoms, or the clinical sequelae of a suspected drug-drug interaction.
- Medication error, misuse, or abuse of IMP, including signs, symptoms, or clinical sequelae.

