10.3.1.3. Events Not Meeting the AE Definition

- Any clinically significant abnormal laboratory findings or other abnormal safety assessments which are associated with the underlying disease, unless judged by the investigator to be more severe than expected for the participant's condition.
- The disease/disorder being studied or expected progression, signs, or symptoms of the disease/disorder being studied, unless more severe than expected for the participant's condition.
- Planned surgeries and nonsurgical interventions should not be reported as AEs unless the underlying medical condition has worsened during the course of the study.
- Situations in which an untoward medical occurrence did not occur (social and/or convenience admission to a hospital).

Anticipated day-to-day fluctuations of pre-existing disease(s) or condition(s) present or detected at the start of the study that do not worsen.

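### The protocol gives conflicting rules on whether an expected Crohn's flare is an AE, so the AE-discontinuation and registry AE tables depend on which passage a site follows

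*Protocol*

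**What the plan says.** Protocol Section 8.3 sets the recording rule for the period after the first AMAX dose: "site personnel will record any change in the condition(s), including exacerbation of CD, and any new conditions as AEs". It names Crohn's disease (CD) and attaches no condition. The same section adds that "Lack of drug effect is not an AE in clinical studies".

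Appendix 3 speaks twice. Among events that are AEs, Section 10.3.1.2 lists "Exacerbation of a chronic or intermittent pre-existing condition, including either an increase in frequency and/or intensity of the condition" and makes no exception for CD. Among events that are not AEs, Section 10.3.1.3 lists "The disease/disorder being studied or expected progression, signs, or symptoms of the disease/disorder being studied, unless more severe than expected" for the participant's condition.

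Section 2.2.1 describes the natural course of the disease: "intermittent disease flares that are interspersed with periods of remission, are very common in CD".

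For stopping, Section 7.1.2 lists disease worsening apart from safety considerations, and under other reasons says "Study participants and physicians may discontinue the study participation if they perceive no clinical benefit".

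On reporting, Section 9.4.4 says that for the AMAX report alone "a listing and summary of SAEs and AEs leading to permanent discontinuation of study intervention will be created", and that all safety data also feed integrated summaries. SAP Section 5.6 plans the same two event classes, each as a listing and a summary. SAP Appendix 6 adds a registry table of SAEs and of non-serious treatment-emergent events (the Other category).

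**The concern.** Two recording rules apply to the same event and point in opposite directions. Under Section 8.3 a flare is an AE because it is an exacerbation of CD. Under Section 10.3.1.3 the same flare is not an AE if the investigator considers it expected for that participant. Since the protocol itself calls flares very common, many could be judged expected. Appendix 3 does not settle the matter, because its own list of qualifying events sides with Section 8.3.

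What is at stake is the meaning of the counts. The stand-alone report plans only two classes of safety event, and CD worsening is an obvious reason for stopping treatment in this population. If sites follow different passages, the number of AEs leading to permanent discontinuation partly reflects site practice, and so does the number of non-serious AEs in the registry table. The integrated safety data take in the same inconsistency.

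**Working it through.** The plan has no figure to reproduce here, so the check sets the rules side by side for four kinds of event after the first AMAX dose.

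| Event | Sections 8.3 and 10.3.1.2 | Section 10.3.1.3 | Result |
|---|---|---|---|
| Expected, non-serious flare | AE | Can be read as not an AE | Conflict |
| Flare more severe than expected | AE | AE, because the exclusion is lifted | No conflict |
| Flare meeting a seriousness criterion | AE, and an SAE through 8.3.1 | Could be screened out if judged expected, but 10.3.2 still makes it an SAE | Largely protected |
| Stop because of an expected flare | AE leading to discontinuation | No AE; the stop can be put down to no perceived benefit (7.1.2) | Conflict |

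Three points complete the comparison.

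1. **Precedence.** Neither document says which section governs, and neither defines expected or exacerbation for CD.
2. **Lack of effect.** The sentence that lack of drug effect is not an AE does not resolve the conflict. It stands in the section that makes exacerbation recordable, and it does not say where failure to benefit ends and worsening begins.
3. **Seriousness.** Section 8.3.1 builds the SAE on an AE. Section 10.3.2 builds it on any untoward event that meets a criterion such as hospitalisation, with no exclusion for the disease under study. A serious flare is lost only if a site first screens with 10.3.1.3, then applies 8.3.1, and disregards 10.3.2.

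**Scale, by assumption only.** Expected enrolment is 640 to 900 (Protocol Section 9.2). The documents give no rate of stopping for an expected flare, so a range is shown. Participants whose classification is open = assumed rate × enrolment:

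- 1%: 0.01 × 640 = 6.4 and 0.01 × 900 = 9, so about 6 to 9
- 5%: 0.05 × 640 = 32 and 0.05 × 900 = 45
- 10%: 0.10 × 640 = 64 and 0.10 × 900 = 90

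These are the differences between every site following Section 8.3 and every site following Section 10.3.1.3. With mixed practice the shift would be smaller, by an unknown amount.

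**The case against.** The strongest reply is that the passages can be read together: exacerbation is recorded, while expected disease that is not worsening is left out. Section 10.3.1.1 counts exacerbated disease as an AE. The last entry of Section 10.3.1.3 exempts only day-to-day fluctuation without worsening, and planned surgery becomes reportable once the underlying condition has worsened. Section 8.3 is also the passage that names CD. This may well be what the sponsor intends, but it is not stated. Nor does it fit the bullet in question, which exempts "expected progression, signs, or symptoms of the disease/disorder being studied, unless more severe than expected for the participant's condition"; progression is itself a form of worsening.

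A second reply is that the burden is reported elsewhere. Reasons for discontinuation are summarised (Protocol Section 9.4.2.1; SAP Section 5.2), and the SAP tabulates Crohn's-related emergency visits and surgeries, and hospitalisations. That is true and limits the harm. It does not make the AE tables consistent.

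Two stronger readings are tempting and should be resisted.

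- **Serious flares missing from the SAE table.** A reader might infer this in some number. Section 10.3.2 covers such events, and the log for amendment (a) records removal of wording that suggested hospitalisation for the disease under study might not be an SAE, which indicates the sponsor's intent. No count of lost SAEs can be derived from the documents.
- **Undercounting that differs by column.** A reader might infer that flares are more often judged expected in participants re-induced with IV treatment. Nothing in the documents shows how investigators would judge expectedness in either group, and no comparison between intervention groups is planned.

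**Conclusion.** The concern holds for expected flares and for stops caused by them. It is a contradiction between stated recording rules, not a missing detail. The outputs exposed are the listing and summary of AEs leading to permanent discontinuation, the registry table of non-serious AEs, and the integrated safety data. Flares more severe than expected are AEs under every passage.

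The existence of the conflict is certain from the text; its size is not. The figure of about 6 to 90 participants rests wholly on an assumed 1% to 10% stopping for an expected flare and on the extreme case of uniform practice one way or the other.

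The efficacy analyses are not affected by how such a stop is coded. Under SAP Section 5.1.5, stopping for an AE and stopping for no perceived benefit are both handled as discontinuation for reasons other than commercial availability or extraordinary circumstances. The point should be fixed because it is cheap and bears on the few stand-alone safety outputs the study plans.

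**What to change.** - **Protocol.** Reconcile Sections 8.3, 10.3.1.2 and 10.3.1.3 into one recording rule for CD worsening after the first dose. One way is to have the second bullet of 10.3.1.3 defer to 8.3; the choice of rule is the sponsor's. Align the SAE definition in 8.3.1 with that in 10.3.2. State when a stop for CD worsening is coded as an AE and when as lack of benefit.
- **Sites.** Send a short clarification. Query CD hospitalisations, surgeries and discontinuations that have no matching AE. Section 8.10 already has the hospitalisations and surgeries collected, and disposition data hold the reasons for stopping.
- **SAP.** Because data may already have been recorded under mixed readings, show the AE-discontinuation outputs and the registry AE table with and without Crohn's terms.

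The cost is a few sentences of protocol text, a site memo, some queries on existing data and extra rows in a small number of tables. Reported AE counts, including AE discontinuations, may rise. Visits, assessments and treatment are unchanged.
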